#### Baseline definition for concomitant therapies

Concomitant medication taken at baseline is any medication with start date continued or before date of first study medication intake (randomisation date will be used for patients not treated) and end date continued on or after date of first study medication intake (randomisation date will be used for patients not treated).

## 7. PLANNED ANALYSIS

For End-Of-Text (EoT) tables, the set of summary statistics is: N / Mean / standard deviation (SD) / standard error (SE) / Min / lower quartile (Q1) / Median / upper quartile (Q3) / Max. The 1st and 99th percentiles might be substituting minimum and maximum in tables with open-ended values to safeguard against implausible extremes. Final decision will be made at the final BRPM.

Geometric means and gCV will be added to the presentation or replace the presentation of mean, standard error and standard deviation for parameters (e.g. NT-proBNP) that follow a log-normal distribution rather than a normal distribution.

Statistical parameters will be displayed to a defined number of decimal places as specified in the BI guideline “Standards for Reporting of Clinical Trials and Project Summaries” [\(3\)](#)

Tabulations of frequencies for categorical data will include all possible categories and will display the number of observations in a category as well as the percentage (%) relative to the respective treatment group (unless otherwise specified, all patients in the respective patient set whether they have non-missing values or not). Percentages will be rounded to one decimal place. The category missing will be displayed only if there are actually missing values.

Disposition of the patient population participating in the trial will be analysed by treatment groups and presented in the clinical trial report as a frequency distribution. The number of patients participating (screened, randomised, screened but not randomised, etc.) in the study by region, country and, for treated patients, centre, will also be analysed by treatment group and presented as a frequency distribution.

Disposition as required for reporting for the trial in EudraCT will be provided. Enrolment will be summarised by country and by age group for reporting in EudraCT.

The reasons for not randomising screened patients will be summarised descriptively.

The frequency of patients with iPDs will be presented by treatment group for the randomised set. The frequency of patients in different analysis sets will also be analysed for each treatment group.

### 7.1 DEMOGRAPHIC AND OTHER BASELINE CHARACTERISTICS

Only descriptive statistics are planned for this section of the report.

Demographics and baseline characteristics will be analysed based on RS. Demographics will be repeated on the TS if the number of patients in the analysis sets differ by more than 5%. Standard descriptive analysis and summary tables will be presented. These summary tables will include description of variables detailed in [Section 6.4](#). In addition, descriptive analyses of the following continuous variables measured at baseline will be presented: Age, body mass index (BMI), time since HF-diagnosis, systolic blood pressure (SBP), diastolic blood pressure

(DBP), weight, eGFR, NT-proBNP, heart rate. For patients with diabetes at baseline, HbA1c at baseline will be shown descriptively.

## **7.2 CONCOMITANT DISEASES AND MEDICATION**

Only descriptive statistics are planned for this section of the report using the randomised set. Concomitant medication use will be summarised by Anatomical-Therapeutic-Chemical classification level 3 (ATC1-ATC2-ATC3) and preferred name. Summaries will be presented for concomitant therapies taken at baseline and separately those added after baseline.

Separate summaries of use of heart failure-related drugs (e.g. ARNi, beta-blockers, ivabradine, diuretics, ACE-inhibitors, ARBs, MRAs, cardiac glycosides), anticoagulants, acetylsalicylic acid (ASA), or lipid lowering drugs at baseline and separately those for added after baseline will be presented. Definitions of these medication groups are based on World Health Organization Drug Dictionary (WHO DD) and are stored in the Project Data Management and Analysis Plan (PDMAP).

Use of devices at baseline will also be summarised.

Concomitant diseases will be summarised by system organ class and preferred term. Relevant medical history by treatment group will also be presented. Both summaries will be presented using the randomised set.

The number and percentage of patients receiving the best tolerated treatment for HF symptoms and other common concomitant diseases or symptoms (e.g. hypertension, diabetes, cardiac arrhythmia, fluid retention) according to prevailing guidelines in the opinion of the investigator will be reported.

## **7.3 TREATMENT COMPLIANCE**

Only descriptive statistics are planned for this section of the report. The number and percentage of patients with overall study medication compliance will be reported.

## **7.4 PRIMARY ENDPOINT**

### **7.4.1 Primary analysis of the primary endpoint**

The primary endpoint ‘change from baseline to week 12 in exercise capacity’ as measured by the change from baseline to week 12 in distance walked in 6 minutes will be evaluated using a normal approximation of the Wilcoxon rank test using the randomised set.

For estimation of effect, non-parametric Hodges-Lehmann estimate for the median difference will be used. Corresponding 95% confidence intervals will be displayed. Any confirmatory conclusion such as for hierarchical testing will be based on the result of the Wilcoxon rank test and will not consider the Hodges-Lehmann estimate or the corresponding confidence interval, which are given to support interpretation.

If no 6MWT is available at week 12, an imputed value as defined in Section 7.5 of the CTP will be used.

The primary analysis will be conducted on all randomised patients, regardless of whether on or off-treatment on the day of 6MWT assessment. Where more than one measurement is available for the same day (duplicate measurements), the longest distance walked will be used for analysis. In case more than one 6MWT results in the same distance walked, the first assessment will be used for analysis.

#### **7.4.2 Sensitivity analysis of the primary endpoint**

Sensitivity analysis for the primary endpoint will include;

- a mixed model repeated measure analysis (MMRM) without imputation of missing values (OC-AD).
- an MMRM restricted to on-treatment values (OC-OT).

The model will include visit-by-treatment interaction and baseline-by-visit interaction. An unstructured covariance structure will be used to model the within-patient errors. Descriptive statistics will be calculated for the value at visit and change from baseline based on OC-AD on the randomised set and based on OC-OT on the treated set. The MMRM analyses will also be shown graphically.

The primary analysis will be repeated restricted to patient in the sensitivity analysis set SensRS1, SensRS2 and SensRS3.

If the mean difference between the treatment groups in 6MWT is above 15m at baseline, the primary analysis will be repeated, but using the ranks of the residuals from the following linear regression model

$$6MWT_{12weeks} \sim 6MWT_{Baseline}$$

with patients without week 12 data ranked below any patient with week 12 assessment similar to the rules for primary analysis.

#### **7.4.3 Subgroup analysis of the primary endpoint**

The primary analysis of the primary endpoint will be repeated for each subgroup as defined in [Table 6.4: 1](#). A forest plot summarising all subgroup analyses will be shown.

### **7.5 SECONDARY ENDPOINTS**

#### **7.5.1 Key secondary endpoints**

*If the null hypothesis for the primary analysis of the primary endpoint is rejected, and the result is more favourable for empagliflozin, superiority is concluded in the primary endpoint, and the overall type I error is preserved for the test in the next step. In the next step a Hochberg procedure will be applied to account for multiplicity of testing of the key secondary endpoints:*

If the largest p-value of the primary analysis of the two key secondary endpoints is below 5%, both null hypotheses of the key secondary endpoints will be rejected. Otherwise, if the smaller p-value of the primary analysis of the two key secondary endpoints is below 2.5%, only the corresponding null hypothesis can be rejected.

If the primary hypothesis of the primary endpoint is not rejected, the tests of the key secondary endpoints are conducted in an exploratory manner.

#### 7.5.1.1 Primary analysis of the key secondary endpoints

*The two key secondary endpoints ‘Change from baseline to week 12 in KCCQ-TSS’ and ‘Change from baseline to week 12 in CHQ-SAS dyspnea score’ are part of the testing strategy.*

*Both key secondary endpoints ‘Change from baseline to week 12 in heart failure symptoms as measured by the KCCQ TSS’ and ‘Change from baseline to week 12 in CHQ-SAS dyspnea score’ will be evaluated using a normal approximation of the Wilcoxon rank test using the randomised set. For estimation of effect the non-parametric Hodges-Lehmann estimate for the median difference will be calculated.*

*Change from baseline in both scores will be defined as the endpoint value at week 12 minus the last available endpoint value before start of randomised trial medication.*

If no questionnaire is available at week 12, an imputed value as defined in [Section 6.6](#) will be used.

#### 7.5.1.2 Sensitivity analysis of the key secondary endpoints

Sensitivity analysis for the key secondary endpoint will include

- a mixed model repeated measure analysis without imputation of missing values (OC-AD).
- a mixed model repeated measure analysis restricted to on treatment values (OC-OT).

The model will include visit-by-treatment interaction and baseline-by-visit interaction. An unstructured covariance structure will be used to model the within-patient errors. Descriptive statistics will be calculated for the value at visit and change from baseline based on OC-AD on the randomised set and based on OC-OT on the treated set.

The primary analysis will be repeated restricted to patients in sensitivity analysis sets SensRS2 and SensRS3.

#### 7.5.1.3 Subgroup analysis of the key secondary endpoints

The primary analysis of the key secondary endpoints will be repeated for each subgroup as defined in [Table 6.4: 1](#). A forest plot summarising all subgroup analyses will be shown.

#### 7.5.1.4 Further exploratory analyses of the key secondary endpoints

A minimal clinically meaningful within-patient change in scores (i.e. responder threshold) will be estimated from the trial population (both treatment groups pooled) for KCCQ-TSS and CHQ-SAS dyspnea as described in [Appendix 9.3](#).

A responder analysis using a chi-square test will be evaluated in addition. The response threshold will be determined as defined in [Appendix 9.3](#).

An empirical cumulative distribution function of descriptive change from baseline to week 12 by treatment group on OC-AD on the randomised set will be shown.

### 7.5.2 Other Secondary endpoints

*Other secondary endpoints will not be part of the testing hierarchy.* No correction for multiple testing of the other secondary endpoints will be made.

*Change from baseline to week 6 in exercise capacity as measured by the distance walked in 6 minutes will be evaluated using the same model as for the primary endpoint.* If no 6MWTD is available at week 6, an imputed value as defined in [Section 6.6](#) will be used.

All other secondary endpoints will take into account all data, regardless of whether the patient was on treatment or not, and without imputation of missing values (OC-AD).

The other continuous endpoints are generally analysed in an MMRM, including visit-by-treatment interaction and baseline-by-visit interaction. An unstructured covariance structure will be used to model the within-patient errors. The MMRM analyses will also be shown graphically.

Descriptive statistics will be calculated for the value at visit and change from baseline.

Shift from baseline score to 12 week score will be tabulated descriptively for single items collected in the context of the clinical congestion score (dyspnea, orthopnea, fatigue, jugular venous distension, rales and edema).

The endpoint “Change from baseline in NT-proBNP at week 12” (after log-transformation) will be evaluated using an MMRM analysis over time with baseline log-transformed NT-proBNP by visit interaction and visit by treatment interaction as covariates without imputation of missing values. Estimates obtained from the model will then be back-transformed and reported on the original scale. The MMRM analyses will also be shown graphically.

Proportion of patients in every category of global impression of change at week 12 will be evaluated using Cochran-Mantel-Haenszel test on the difference in mean treatment scores, using modified ridit scores.

Proportions of patients categorised by the difference in scores between baseline and week 12 in patient global impression of severity score will be evaluated using a Cochran-Mantel-Haenszel test on the difference in mean treatment scores, using modified ridit scores. Difference in score will be defined as the number of categories improved/deteriorated from baseline. Shift from baseline score to 12 week score will be tabulated descriptively.

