### 5.1.9 Patient Global Impression of Severity of Heart Failure Symptoms

Patient global Impression of Severity (PGI-S) of Heart Failure Symptoms is a 1-item questionnaire to assess patient's impression of symptoms severity, specifically: shortness of breath, fatigue and swelling.

The PGI-S asks the patient to choose one response that best describes how his/her Heart Failure Symptoms, specifically: shortness of breath, fatigue and swelling are now on a 5-point scale:

- Not at all (1)
- Mild (2)
- Moderate (3)
- Severe (4)
- Very severe (5)

Please refer to [section 6.2.2](#) for order of completion of patient reported outcome measure and [Appendix 10.3.5](#).

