#### Other secondary endpoints

Change from baseline to week 6 in exercise capacity as measured by the distance walked in 6 minutes will be evaluated using the same model as for the primary endpoint.

Change from baseline of Clinical Congestion Score at week 12 will be evaluated using an mixed model repeated measure analysis (MMRM) analysis over time. The model will include the factor treatment and the linear covariate of baseline Clinical Congestion Score.

Proportion of patients in every category of global impression of change at week 12 will be evaluated using Cochran-Mantel-Haenszel test. Details on combining categories if the proportion of patients in one of the categories is small will be given in the TSAP.

Proportions of patients categorized by the shift in scores between baseline and week 12 in patient global impression of severity score will be evaluated using Cochran-Mantel-Haenszel test. Details on combining categories if the proportion of patients in one of the categories is small will be given in the TSAP.

The endpoint “Change from baseline in NT-proBNP at week 12” (after log-transformation) will be evaluated using a MMRM analysis over time with baseline log-transformed NT-proBNP as a covariate without imputation of missing values.

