	no atrial fibrillation at baseline and < / ≥ median			

Table 6.4: 1 Categories of covariates for displays of baseline characteristics and subgroup analyses (cont.)

Variable	Categorisation	Demo- graphics 	Subgroups for Efficacy endpoints 	Safety
Baseline KCCQ-TSS	By quartiles		X (only KCCQ-TSS and 6MWT)	
Baseline CHQ-SAS Dyspnea domain	By quartiles		X (only CHQ- SAS dyspnea and 6MWT)	
Baseline PGI-S Dyspnea	5 categories	X	X (only CHQ- SAS dyspnea)	
Baseline PGI-S HF symptoms	5 categories	X	X (only KCCQ-TSS)	
Baseline distance walked in 6 minutes	< / >= median		X (only 6MWT)	
Baseline use of ACE- inhibitor, ARB or ARNi	Yes / No	X 	X	
Baseline use of diuretics other than MRA	Yes / No	X 	X	
Baseline use of MRA	Yes / No	X 	X	
Baseline use of loop or high-ceiling diuretics	Yes / No	X 	X	
Baseline haemoglobin	< / >= median		X	

1 The column demographics shows categories displayed for overall demographics.

Demographics are not planned by subgroup.

2 Subgroups planned for the following endpoints: primary and key secondary endpoints.

3 Region categorisation: see [Table 9.1: 1](#).

4 Diabetes at baseline categorisation: see [Table 9.2: 1](#); for subgroup analysis ‘pre-DM’ and ‘non-DM (excluding pre-DM)’ will be combined into the category ‘non-DM’

5 atrial fibrillation at baseline means atrial fibrillation in last ECG before treatment intake

6 patients with NYHA class I are counted in subgroup NYHA class II

7 Median NT-proBNP will be calculated for randomised patients with/without atrial fibrillation at baseline separately and subgroups will be defined based on the respective median for patients with/without atrial fibrillation at baseline accordingly

8 part of the presentation of baseline concomitant therapy as outlined in [Section 7.2](#)

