### 7.6.2 Ordinal endpoints

The following endpoints will be evaluated using the same models as defined for the corresponding secondary endpoints:

- Change from baseline in Patient Global Impression of Severity of Heart Failure Symptoms at week 6.
- Change from baseline in Patient Global Impression of Severity of Dyspnea at week 6.
- Patient Global Impression of Change in Heart Failure Symptoms at week 6.

- Patient Global Impression of Change in Dyspnea at week 6.
- Change from baseline in Clinician Global Impression of Severity of Chronic Heart Failure (CHF) at Week 6 and week 12
- Clinician Global Impression of Change in CHF Severity at Week 6 and week 12

Frequencies and proportions of patients categorised descriptively by the

- shift in NYHA class from baseline to week 6 and to week 12.

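### Stratifying the CMH tests of change in PGI-S and clinician severity by the baseline category would gain precision at almost no cost (exploratory endpoints only)

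*SAP*

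**What the plan says.** Protocol 7.3.2 (Other secondary endpoints) assigns a Cochran-Mantel-Haenszel (CMH) test to this comparison: "Proportions of patients categorized by the shift in scores between baseline and week 12 in patient global impression of severity score". It names no stratum and leaves the combining of small categories to the SAP.

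SAP 7.5.2 says that the severity change "will be evaluated using a Cochran-Mantel-Haenszel test on the difference in mean treatment scores, using modified ridit scores", and adds: "Difference in score will be defined as the number of categories improved/deteriorated from baseline". It names no stratum either. The starting category is kept only in a display: "Shift from baseline score to 12 week score will be tabulated descriptively".

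SAP 7.6.2 extends the method: "The following endpoints will be evaluated using the same models as defined for the corresponding secondary endpoints". That covers both PGI-S scales at week 6 and clinician global severity at weeks 6 and 12. With the two week-12 PGI-S endpoints, six tests are affected.

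PGI-S is bounded: Protocol 5.1.9 has the patient rate how "shortness of breath, fatigue and swelling are now on a 5-point scale". The baseline category is already a derived variable. SAP Table 6.4: 1 lists "Baseline PGI-S HF symptoms" in five categories as a subgroup factor for KCCQ-TSS, and baseline PGI-S dyspnea likewise for CHQ-SAS dyspnea. Randomisation is unstratified (Protocol 7.6).

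**The concern.** The room to change depends on where the patient starts. A patient at *Not at all* cannot improve, one at *Mild* can improve by a single category, and one at *Very severe* cannot worsen. A single-stratum test puts all their differences into one ranking. Ridit scoring does not help, because it ranks the differences without reference to the starting point.

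Two things follow. Spread in the baseline adds noise to the comparison. And if the arms differ by chance at baseline, regression to the mean moves their changes apart even when the drug does nothing. The SAP recognises this second problem for the primary endpoint: section 7.4.2 adds a baseline-adjusted rank analysis if mean baseline walking distance differs by more than 15 m. The severity scales have no such safeguard.

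At stake is the precision of six exploratory p-values on symptom severity. No confirmatory claim is involved.

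**Working it through.** **The plan's own figure.** The documents give no power or sample size for PGI-S. The nearest figure is the primary Wilcoxon test (Protocol 7.7: 30 m, SD 72 m, two-sided 5%, 90% power). P(X<Y) = Φ(−30/(72√2)) = Φ(−0.295) = 0.384. Then n = (1.960 + 1.282)² / (6 × 0.1159²) ≈ 130.4, rounded up to 131 per group, as stated. This confirms the trial's inputs but says nothing about PGI-S.

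**Analytic check.** Take baseline and follow-up as standardised with correlation ρ.
- Variance of the change: 2(1−ρ). Variance given baseline: 1−ρ². The ratio is 2/(1+ρ), or 1.54, 1.33 and 1.18 at ρ = 0.3, 0.5 and 0.7.
- A baseline imbalance d shifts the mean change by (1−ρ)d. At ρ = 0.5 half of it carries over, and the share falls as ρ rises.

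**Simulation inputs.**
- From the documents: 1:1 allocation, five categories, no imputation for these endpoints, and 150 per arm with about 5% missing (150 × 0.95 = 142.5, taken as 142).
- Assumed: a latent bivariate normal cut into five categories, baseline mix 5/30/45/17/3% or a floor-heavy 15/45/30/8/2%, a common improvement of 0.2 latent SD in both arms, a treatment effect of 0.30 latent SD, and ρ as shown. There were 4,000 trials per scenario.
- Planned test: single-stratum CMH mean-score test with modified ridits on the category difference, which is equivalent to a Wilcoxon test. Alternative: the same statistic summed over baseline categories, with ridits computed within each.
- Relative efficiency: squared ratio of the mean z statistics. At ρ = 0.5, for example, (2.563/2.183)² = 1.38.

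| Baseline mix | ρ | Planned power | Stratified power | Relative efficiency |
|---|---|---|---|---|
| 5/30/45/17/3 | 0.3 | 48% | 66% | 1.58 |
| 5/30/45/17/3 | 0.5 | 59% | 73% | 1.38 |
| 5/30/45/17/3 | 0.7 | 75% | 84% | 1.26 |
| 15/45/30/8/2 | 0.3 | 44% | 67% | 1.70 |
| 15/45/30/8/2 | 0.5 | 54% | 72% | 1.49 |
| 15/45/30/8/2 | 0.7 | 72% | 84% | 1.32 |

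Repeat runs at 0.30 SD agreed within about a point and gave 91% against 94% at ρ = 0.85. With a smaller effect of 0.2 SD and ρ of 0.85 to 0.90, stratifying gained 5 to 9 points (relative efficiency 1.12 to 1.21). Merging the sparse end categories gave 65%, 72% and 83% at ρ = 0.3, 0.5 and 0.7, against 67%, 73% and 84% unmerged in the same runs.

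**Type I error.** Overall it was 4.5% to 5.6% for the planned test and 4.7% to 5.3% for the stratified one.

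**Chance imbalance.** With the first mix, the baseline SD is 0.87 category, so the standard error of the difference in means is 0.87 × √(2/142) = 0.104. A difference of at least 0.15 category is then 1.45 standard errors, expected in about 15% of trials; the simulation gave 14%. In those trials, with no drug effect and ρ = 0.5, the planned test rejected 13% of the time and the stratified test 5%. Across all runs the figures were about 8 to 16% against 4 to 6%.

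**The case against.** Much of the case for leaving the plan alone stands.

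- A one-stratum CMH mean-score test is a legitimate ordinal test. It holds its level under randomisation, and no design stratum has been dropped.
- SAP 7.5.2 puts these endpoints outside the hierarchy, and the documents set no power target for them.
- A reader might infer that the plan treats the ordinal endpoints less carefully than the rest, because the MMRMs adjust for baseline. The documents do not support that. The primary and key secondary tests (SAP 7.4.1 and 7.5.1.1) are also rank tests on change without baseline adjustment, so the severity tests follow the same non-parametric approach.
- A reader might infer that a baseline imbalance enters the result in full. It does not: the baseline is subtracted, so only the regression-to-the-mean part remains. The starting category is also shown in the shift table.
- The size of the gain rests on inputs that the documents do not give, and it is small if the correlation is high.
- Patients must be clinically stable and in NYHA class II to IV, so the end categories could be thin. A stratum with patients from one arm only contributes nothing.

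None of this gives a reason to prefer the single-stratum test when the baseline category is already collected and coded. The point about sparse strata is met by a merging rule.

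**Conclusion.** This is a free improvement to exploratory endpoints, not an error. The planned test is valid but less efficient than the stratified one in every scenario tried. With a latent effect of 0.30 SD and the first baseline mix, the gain is about 18 to 19 points of power at ρ = 0.3, 14 at 0.5, 9 at 0.7 and 3 at 0.85. It reaches 23 points with the floor-heavy mix at ρ = 0.3. The sizes are illustrative; the direction was the same throughout.

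Three limits apply. The SAP does not say that the test is unstratified; that is the reading when no stratum is named, and if strata were intended the SAP still needs to name them. Stratifying does not remove the floor and ceiling of the scale; it compares patients who have the same room to move. And a reader might extend the advice to the Patient Global Impression of Change tests. Those scales rate change directly and have no baseline of their own, and no gain has been shown for them.

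**What to change.** Add to SAP 7.5.2, and so by reference to 7.6.2, that the CMH mean-score test for change in PGI-S and in clinician severity is stratified by the baseline category of the same scale, with modified ridits computed within strata.

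Add a merging rule, fixed before unblinding. When an end category is sparse, merge *Not at all* with *Mild*, or *Severe* with *Very severe*, and the equivalent clinician severity categories. The threshold has to be stated; the 14-patient minimum that SAP 6.4 uses for subgroups is one candidate.

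The cost is a sentence or two in the SAP and one extra term in the SAS TABLES statement. No new data are needed. The descriptive shift table and the tests of global impression of change stay as they are.
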